13.6.6.4 Sensitivity Analyses

All sensitivity analyses will be performed on the PP Analysis Set unless otherwise specified.

13.6.6.4.1 TDT Population

Proportion of subjects who are transfusion-free (independent) for ≥ 12 weeks during treatment

The number and percentage of subjects who remain transfusion independent for at least 12 weeks during treatment will be tabulated, along with summary statistics of the duration of transfusion independence in weeks. The proportion of subjects who are transfusion independent for at least 12 weeks during treatment will also be analyzed using CMH tests. ORs, 95% CIs, and p-values will be reported. The difference in proportions (active arm-Placebo and the combined active arms-Placebo) and corresponding 95% CI will be also provided. A bar plot will be provided, including both the proportions of subjects who are transfusion-free for ≥ 8 weeks and ≥ 12 weeks.

13.6.6.4.2 NTDT Population

Proportion of subjects who are transfusion-free (independent) for ≥ 12 weeks during treatment

The number and percentage of subjects who remain transfusion independent for at least 12 weeks during treatment will be tabulated, along with summary statistics of the duration of transfusion independence in weeks. The proportion of subjects who are transfusion independent for at least 12 weeks during treatment will also be analyzed using CMH tests. ORs, 95% CIs, and p-values will be reported. The difference in proportions (active arm-Placebo and the combined active arms-Placebo) and corresponding 95% CI will be also provided. A bar plot will be provided, including both the proportions of subjects who are transfusion-free for ≥ 8 weeks and ≥ 12 weeks.

13.6.7 Specialty Hematology Endpoints

Specialty hematology laboratory assessments will be summarized and listed using the ITT and Per-Protocol Analysis sets similarly but separately for each population. Assessments will include:

- HbF
- F-cells (%)

Descriptive statistics (N, mean, SD, median, Q1, Q3, minimum, and maximum) for the observed and change from Baseline values will be presented at Baseline and each post-Baseline collection.

Specialty hematology tabulations will be repeated stratified by genotype (concomitant alpha gene deletion vs. concomitant alpha gene duplication vs. concomitant alpha gene triplication).

The following figures will be provided for all specialty hematology parameters:

- Shift plot from Baseline to post-Baseline maximum for each specialty hematology parameter by treatment arm and for the combined IMR-687 treatment arms;
- Box and whisker plot for each specialty hematology parameter by visit for each treatment arm and the combined IMR-687 treatment arms

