### 6.3.2. Population 2: Non-transfusion Dependent $\beta$ -Thalassemia

The exploratory objectives in NTDT subjects are:

- To characterize the PD profile of IMR-687 versus placebo with respect to erythropoiesis, iron metabolism, and hemolysis.
- To evaluate the effect of IMR-687 versus placebo on functional and health-related QoL.
- To evaluate the effect of IMR-687 versus placebo on  $\beta$ -thalassemia-related symptoms and severity.
- To evaluate responses to IMR-687 per genotypes in subjects with NTDT.

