### 8.1. Inclusion Criteria

Subjects must meet **all** of the following criteria to be eligible for the study:

1. Subjects must understand and voluntarily provide informed consent and sign an ICF prior to any study-related assessments/procedures being conducted. Although RBC transfusions and associated Hb laboratory measurements prior to Screening are not study related, the ICF will specifically request subject consent to collect these data.
2. Subjects must be  $\geq 18$  to  $\leq 65$  years of age at the time of signing the ICF.
3. Subjects must have documented diagnosis of  $\beta$ -thalassemia or HbE/ $\beta$ -thalassemia in their medical history. Concomitant alpha gene deletion, duplication, or triplication is allowed.
4. **For TDT subjects only:** Subjects must be regularly transfused, defined as  $>3$  to  $10$  pRBC units† in the 12 weeks prior to the Baseline (Day 1) visit and no transfusion-free period for  $>35$  days during that period.

**For NTDT subjects only:** Subjects must be transfusion independent, defined as  $0$  to  $\leq 3$  units† of pRBCs received during the 12-week period prior to the Baseline (Day 1) visit, must not be on a regular transfusion program, must be RBC transfusion-free for at least  $\geq 4$  weeks prior to randomization, and must not be scheduled to start a regular hematopoietic stem cell transplantation within 9 months.

5. Subjects must have documentation of the dates of transfusion events and the number of pRBC units per event within the 12 weeks prior to the Baseline (Day 1) visit.
6. Subjects must be willing and able to complete all study assessments and procedures, and to communicate effectively with the investigator and site staff.
7. Subjects must have Eastern Cooperative Oncology Group (ECOG) performance score of  $0$  to  $1$  ([Appendix 1](#)).
8. Female subjects must not be pregnant or breastfeeding and be highly unlikely to become pregnant. Male subjects must be unlikely to impregnate a partner. Male or female subjects must meet at least one of the following criteria:
  - A female subject who is not of reproductive potential is eligible without requiring the use of contraception. A female subject who is not of reproductive potential is defined

---

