13.4 Demographic and Baseline Characteristics

By-population tabulation summaries and by-subject listings of demographics, baseline characteristics, disease history, and historical transfusion burden will be presented in the Safety Analysis Set.

The demographic and baseline characteristics consist of:

- Age (years) –as numeric value
- Sex (Female, Male)
- Ethnicity (Categories as collected from CRF)
- Race (Categories as collected from CRF)
- Height (cm)
- Weight (kg)
- BMI (kg/m^2)
- Baseline Eastern Cooperative Oncology Group (ECOG) Score (0, 1)
- Region (Europe/North America, Asia/Africa) (see Appendix 5 for countries included in each region)
- Beta Thalassemia Diagnosis (Major, Intermediate, E)
- Concomitant Alpha Gene Status (Deletion, Duplication/Triplication, No Alpha)

- Previous/Ongoing Cardiac and/or Hepatic Co-morbidities due to Iron Overload (TDT) (Yes, No)
- Baseline Transfusion Burden in Packed RBC Units (day -83 to 1) continuously and categorically categorized level: Low Transfusion Burden (≤ 5), Medium Transfusion Burden ($> 5 < 7$) and High Transfusion Burden (> 7) [TDT]
- Pre-transfusion Hemoglobin Threshold, defined as mean of all documented pre-transfusion hemoglobin values during the 12 weeks prior to Dose 1 Day 1 (continuous and categorized level: < 9 g/dL and ≥ 9 g/dL) [TDT]
- Baseline Serum Ferritin –as numeric value
- Daily Iron Chelation Use (Yes, No)
- Splenectomy (Yes, No)
- Baseline Hemoglobin (≤ 8.5 , > 8.5) [NTDT]

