13.6.8 Pharmacodynamic Endpoints

Pharmacodynamic laboratory assessments will be summarized and listed using the Per Protocol, ITT, and mITT Analysis sets, for the TDT population. Assessments will include:

- Iron Metabolism

- Serum ferritin
- Hepcidin-25
- Serum iron and total iron binding capacity (TIBC) for calculated transferrin saturation
- Erythropoiesis
 - Erythropoietin
 - Soluble transferrin receptor (STFR)
- Hemolysis
 - Haptoglobin
 - LDH
 - Indirect Bilirubin
 - Reticulocytes (absolute and %)
- Cardiac/inflammation
 - Serum N-terminal pro-B-type natriuretic peptide (serum NT-proBNP)
 - High-sensitivity C-reactive protein (hsCRP)
- Adhesion
 - Soluble E-selectin
 - Soluble P-selectin
 - Soluble intercellular adhesion molecule 1 (ICAM-1)
 - Vascular cell adhesion molecule 1 (VCAM-1)
- Hematology
 - RDW
 - MCV
 - Hb

Descriptive statistics (N, mean, SD, median, Q1, Q3, minimum, and maximum) for the observed and change from Baseline values will be presented at Baseline and each post-Baseline collection.

PD tabulations will be repeated stratified by genotype (concomitant alpha gene deletion vs. concomitant alpha gene duplication vs. concomitant alpha gene triplication) and Beta-Thalassemia Major (B0 / B0, B0 / B+), Beta-Thalassemia Intermedia (B+ / B+, B0 / B+, B+ / B, B0 / B, B0 / B0), and HbE/Beta-Thalassemia (BE / B+, BE / B0).

The following figures will be provided for all PD parameters:

- Shift plot from Baseline to post-Baseline maximum for each PD parameter and treatment arm and for the combined IMR-687 treatment arms;
- Box and whisker plot of PD parameters by visit and treatment arm and the combined IMR-687 treatment arms.

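### The alpha-gene strata in SAP 13.6.7 and 13.6.8 have no place for subjects without an alpha-gene change

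*SAP*

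**What the plan says.** Three SAP sections set out categories of alpha-gene status.

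- SAP 13.4, baseline characteristics: "Concomitant Alpha Gene Status (Deletion, Duplication/Triplication, No Alpha"). There are three levels. Gains are merged, and subjects with no alpha-gene change have their own level.
- SAP 13.6.7, HbF and F cells: the tables are repeated "stratified by genotype (concomitant alpha gene deletion vs. concomitant alpha gene duplication vs. concomitant alpha gene triplication"). There are three levels, gains are split, and there is no level for an unchanged alpha gene. No other genotype split appears in that section.
- SAP 13.6.8, PD markers: "PD tabulations will be repeated stratified by genotype (concomitant alpha gene deletion vs. concomitant alpha gene duplication vs. concomitant alpha gene triplication"). The alpha levels are the same as in 13.6.7, but the sentence goes on "and Beta-Thalassemia Major (B0 / B0, B0 / B+), Beta-Thalassemia Intermedia" and ends "and HbE/Beta-Thalassemia (BE / B+, BE / B0"), so beta-genotype strata are added.

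On eligibility, Protocol 8.1 (criterion 3) says: "Concomitant alpha gene deletion, duplication, or triplication is allowed". On purpose, Protocol 6.3.2 gives as an exploratory objective "To evaluate responses to IMR-687 per genotypes in subjects with NTDT", and Protocol 6.3.1 has the matching objective for TDT. The endpoint tables in Protocol 6.4 and SAP 9.0 also list biomarker change by genotype for both populations. The SAP footnotes that entry to 13.6.8 for the list of biomarkers.

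**The concern.** A set of strata should give every subject in the analysis set one place. The list in 13.6.7 and 13.6.8 covers only subjects who carry some alpha-gene change, yet carrying one is optional at entry and the SAP itself defines a category for those who do not. A programmer following the text would either leave those subjects out of the alpha split or have to improvise a row.

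What is at stake is what the split can show. To learn whether alpha status goes with a different HbF or PD response, one needs subjects with and without a change side by side. With the second group absent, the tables can only compare deletion, duplication and triplication with one another. A reader adding up the strata would also find that they do not reach the analysis-set total, with no explanation.

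**Working it through.** The point concerns the categories of descriptive tables, so there is no power, alpha or sample-size figure to reproduce. The check is whether each list covers every eligible subject.

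| Place | Alpha levels | Level for no alpha change? | Beta strata? | Where a subject with no alpha change goes |
|---|---|---|---|---|
| SAP 13.4 (baseline) | Deletion; Duplication/Triplication; No Alpha | Yes | Not in this item | No Alpha |
| SAP 13.6.7 (HbF, F cells) | Deletion; Duplication; Triplication | No | None | No genotype stratum |
| SAP 13.6.8 (PD markers) | Deletion; Duplication; Triplication | No | Major; Intermedia; HbE/beta | Beta stratum only |

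Step 1. Can such subjects be enrolled? Yes. Criterion 3 requires beta-thalassemia or HbE/beta-thalassemia and only permits an alpha-gene change.

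Step 2. Does the SAP expect them? Yes, since 13.4 names a level for them.

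Step 3. Is the gap filled elsewhere?

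- The subgroup lists in SAP 13.6.4.5 contain beta mutation (TDT only), diagnosis, BCL11A and XMN1. Alpha status is not among them.
- SAP Tables 11 and 12 list pharmacogenomic analyses that include alpha-globin (a descriptive summary, plus subgroup analysis for NTDT), but give no alpha levels and do not name HbF or the PD markers as the outcome.
- For HbF in TDT, 13.6.7 is the only genotype split that the SAP specifies, because the TDT subgroup endpoints in 13.6.4.5 are all transfusion-burden endpoints.

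So no section explicitly tabulates HbF or PD response by alpha status with the unchanged group included.

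Step 4. How many subjects? With about 60 subjects per population and a share p known to carry an alpha-gene change, 60 × (1 − p) would have no alpha stratum. The documents do not give p, so the count cannot be worked out.

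Step 5. Can status be unknown? Possibly. Protocol 11.1.8 makes the pharmacogenomic sample, which covers alpha-globin, optional. Adding only a No Alpha level might therefore still leave some subjects without a row.

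**The case against.** The best case on the other side is that this is a wording mismatch with little consequence, and several parts of that case stand.

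- A reader might infer that subjects without an alpha-gene change drop out of all the genotype tables. For the PD markers the text does not support that, because 13.6.8 also stratifies by Major, Intermedia and HbE/beta. The biomarker-by-genotype endpoint in SAP 9.0 refers to 13.6.8, so for the markers it names these subjects are still tabulated by genotype.
- Response by genotype does not rest on these two sections alone. SAP 13.6.4.5 plans diagnosis, BCL11A and XMN1 subgroups in both populations, plus beta mutation in TDT. For NTDT these include mean change in Hb and HbF. Protocol 11.1.8 allows pharmacogenomic results to be reported separately.
- A reader might treat subjects with no alpha change as a formal reference group. The documents name no reference genotype and plan no test between strata.
- A reader might suppose that most subjects are lost, or that splitting the gains matters because they are rare. The documents give no frequency for either.

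What this case does not answer is the omission itself. Both alpha lists leave out a level that 13.4 defines, and none of the other planned analyses sets out HbF or PD response by alpha status with that level present.

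**Conclusion.** The point holds in limited form. The alpha stratification in both sections is incomplete against the eligibility rule and against SAP 13.4. In 13.6.7, subjects with no alpha-gene change have no genotype stratum; in 13.6.8 they have no alpha stratum but keep a beta stratum. The duplication and triplication grouping also differs from 13.4.

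The consequence is minor. These are exploratory, descriptive tables, everyone stays in the unstratified versions, and neither the primary safety objective nor any planned comparison between arms is touched. What is lost is any view of subjects with an alpha-gene change against those without.

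The conclusion rests on two readings. One is that No Alpha in 13.4 means no concomitant alpha-gene change, which is its evident sense. The other is that the alpha and beta lists in 13.6.8 are separate sets of strata. A reader might take them as crossed, which would leave these subjects with no PD stratum either; the sentence lists the two sets one after the other and says nothing of crossing them.

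**What to change.** In SAP 13.6.7 and 13.6.8, replace the alpha list with the 13.4 levels: No Alpha, Deletion, Duplication/Triplication. Add an Unknown/not tested row so that the alpha strata sum to the analysis set. Keep the beta-genotype strata in 13.6.8, and state that the alpha and beta splits are tabulated separately.

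The cost is a few words in two SAP sections and the matching table shells. The three-level variable is already planned for the baseline table, so no new data collection, no new derivation for the main levels and no protocol amendment is needed. The tables may still be sparse in the levels with an alpha change. The fix makes them complete and consistent; it does not make them precise.

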13.6.8 Pharmacodynamic Endpoints

Pharmacodynamic laboratory assessments will be summarized and listed using the Per Protocol, ITT, and mITT Analysis sets, for the TDT population. Assessments will include:

- Iron Metabolism

- Serum ferritin
- Hepcidin-25
- Serum iron and total iron binding capacity (TIBC) for calculated transferrin saturation
- Erythropoiesis
 - Erythropoietin
 - Soluble transferrin receptor (STFR)
- Hemolysis
 - Haptoglobin
 - LDH
 - Indirect Bilirubin
 - Reticulocytes (absolute and %)
- Cardiac/inflammation
 - Serum N-terminal pro-B-type natriuretic peptide (serum NT-proBNP)
 - High-sensitivity C-reactive protein (hsCRP)
- Adhesion
 - Soluble E-selectin
 - Soluble P-selectin
 - Soluble intercellular adhesion molecule 1 (ICAM-1)
 - Vascular cell adhesion molecule 1 (VCAM-1)
- Hematology
 - RDW
 - MCV
 - Hb

Descriptive statistics (N, mean, SD, median, Q1, Q3, minimum, and maximum) for the observed and change from Baseline values will be presented at Baseline and each post-Baseline collection.

PD tabulations will be repeated stratified by genotype (concomitant alpha gene deletion vs. concomitant alpha gene duplication vs. concomitant alpha gene triplication) and Beta-Thalassemia Major (B0 / B0, B0 / B+), Beta-Thalassemia Intermedia (B+ / B+, B0 / B+, B+ / B, B0 / B, B0 / B0), and HbE/Beta-Thalassemia (BE / B+, BE / B0).

The following figures will be provided for all PD parameters:

- Shift plot from Baseline to post-Baseline maximum for each PD parameter and treatment arm and for the combined IMR-687 treatment arms;
- Box and whisker plot of PD parameters by visit and treatment arm and the combined IMR-687 treatment arms.

13.7 Other Data

Pregnancy test results will be listed on the Safety Analysis Set.

Virology available data will be summarized and listed by treatment group on the Safety Analysis Set. Blood samples will be collected for serum virology (screening assessment) only if clinically indicated. Testing will be performed through a central laboratory and may include hepatitis B surface antigen (HBsAg), hepatitis A immunoglobulin M (IgM), and hepatitis C virus (HCV) antibody, as well as HIV testing.

15.0 Glossary of Abbreviations

Glossary of Abbreviations:

AE	Adverse Event
ANCOVA	Analysis of Covariance
ATC	Anatomic Therapeutic Classification
AUC ₀₋₂₄	Area Under the Concentration-Time Curve from Time 0 to 24 Hours Postdose
AUC _{inf}	Area Under the Concentration-Time Curve from Time 0 to Infinity
AUC _{last}	Area Under the Concentration-Time curve from Time 0 to the Last Measurable Concentration Postdose
BLQ	Below the Limit of Quantification
CI	Confidence Interval
C _{last}	Last Observed Measurable Plasma Concentration
CL/F	Apparent Total Body Clearance from Oral Administration after Single Dose
CL _{ss} /F	Apparent Total Body Clearance from Oral Administration at Steady State
C _{max}	Maximum Plasma Concentration Postdose after Single Dose
C _{max,ss}	Maximum Plasma Concentration Postdose at Steady State
C _{min}	Minimum Plasma Concentration over the Dosing Interval
C _{trough}	Concentration at the End of the Dosing Interval
CMH	Cochran-Mantel-Haenszel
CRF	Case Report Form
CSR	Clinical Study Report
DMC	Data Monitoring Committee
ECG	Electrocardiogram
Hb	Hemoglobin
HbF	Fetal Hemoglobin
IVRS/IVRS	Interactive Voice Response System
Lambda _z	Apparent Terminal Elimination Phase Rate Constant
LLOQ	Lower Limit of Quantification
LSMean	Least squares mean
MedDRA	Medical Dictionary for Regulatory Activities
MMRM	Mixed Model Repeated Measures
NTDT	Non-transfusion dependent
PD	Pharmacodynamic
PK	Pharmacokinetic
PP	Per Protocol

pRBC	Packed red blood cells
PT	Preferred Term
QD	Once daily
QoL	Quality of Life
R _{AUC}	Accumulation Ratio
RBC	Red blood cells
SAP	Statistical Analysis Plan
SAE	Serious Adverse Event
SD	Standard Deviation
SI	International System of Units
SOC	System Organ Class
T _{1/2}	Apparent Terminal Elimination Half-life
T _{last}	Time of Last Measurable Plasma Concentration
T _{max}	Time to Maximum Plasma Concentration Postdose after Single Dose
T _{max,ss}	Time to Maximum Plasma Concentration Postdose at Steady State
TDT	Transfusion dependent
TEAE	Treatment-Emergent Adverse Event
V _{z/F}	Apparent Total Body Clearance from Oral Administration after Single Dose or Steady State

16.0 Appendices

Appendix 1 Schedule of Assessments – TDT Population

	Screening ^b	Baseline	Double-blind, Placebo-controlled Treatment															EOT ^a / ET	End of Study (Safety FU)
Visit number	1	2	3	4	5	6	7	8	9	10	11	12	13	14	15	16	17		
Study Week(s)	-4 to 0	NA	1	2	3	6	9	12	15	18	21	24	27	30	33	36	40		
Study Day(s)	-28 to -1	1 ^b	7 ±2	14 ±2	21 ±7	42 ±7	63 ±7	84 ±7	105 ±7	126 ±7	147 ±7	168 ±7	189 ±7	210 ±7	231±7	252±7	280±7		
On-site visits	X	X	X		X	X	X	X	X	X	X	X	X	X	X	X	X		
Telephone visits ^c				X															
Informed consent	X																		
PGx ICF and blood draw (optional) ^d	X																		
Demographic information	X																		
Medical/disease history ^e	X																		
Inclusion/exclusion criteria	X	X																	
ECOG score	X																		
Clinically indicated virology (Hep A, B, and C and HIV)	X																		
Historical transfusion burden ^f	X	X																	
Randomization		X																	
Vital signs ^g	X	X	X		X	X	X	X	X	X	X	X	X	X	X	X	X		
Weight	X	X	X		X	X	X	X	X	X	X	X	X	X	X	X	X		

	Screening	Baseline	Double-blind, Placebo-controlled Treatment															EOT^a / ET	End of Study (Safety FU)
Visit number	1	2	3	4	5	6	7	8	9	10	11	12	13	14	15	16	17		
Study Week(s)	-4 to 0	NA	1	2	3	6	9	12	15	18	21	24	27	30	33	36	40		
Study Day(s)	-28 to -1	1^b	7 ±2	14 ±2	21 ±7	42 ±7	63 ±7	84 ±7	105 ±7	126 ±7	147 ±7	168 ±7	189 ±7	210 ±7	231±7	252±7	280±7		
Height	X																		
Transfusion burden ^h					X	X	X	X	X	X	X	X	X	X	X	X	X		
Physical examination ⁱ	X	X	X		X	X	X	X	X	X	X	X	X	X	X	X	X		
12-Lead ECG ^j	X	X	X		X	X		X		X		X		X		X	X		
Hematology and Chemistry	X	X	X		X	X		X		X		X		X		X	X		
Coagulation studies	X							X				X				X			
Urinalysis	X	X			X			X				X				X			
Pregnancy testing ^k	X	X	X		X	X	X	X	X	X	X	X	X	X	X	X	X		
Specialty hematology ^l	X	X			X			X		X		X		X		X			
PD markers ^m	X	X			X			X		X		X				X			
IMR-687 plasma PK ⁿ		X	X		X							X				X			
QOL assessments ^o		X						X				X				X			
Study drug dispensing		X			X	X	X	X	X	X	X	X	X	X	X				
Study drug admin at site ^p		X	X		X	X		X		X		X		X		X			
Study drug admin		Oral administration of IMR-687 or placebo qd																	
AEs and concomitant medications	Continuous ^q																		

AE = adverse event; ECG = electrocardiogram; ECOG = Eastern Cooperative Oncology Group; ET= early termination; EOT = end of treatment; FU = follow-up;

Hb = hemoglobin; HbF = fetal hemoglobin; HIV = human immunodeficiency virus; hsCRP = highly sensitive C-reactive protein; ICAM-1 = intercellular adhesion molecule 1; ICF = informed consent form; NT-proBNP = N-terminal pro B-type natriuretic peptide; PD = pharmacodynamics; PE = physical examination; PGx = pharmacogenomics;

PK = pharmacokinetic; pRBC = packed red blood cells; QOL = quality of life; SD = standard deviation; SF-36 = Short Form (36) Health Survey; TEAE = treatment-emergent adverse event; TIBC = total iron binding capacity; TranQOL = Transfusion-dependent QoL Questionnaire; VCAM-1 = vascular cell adhesion molecule 1.

Note: Unless otherwise specified, all assessments should be completed prior to dosing at any given timepoint.

Note: Unscheduled visits may occur, limited to visits resulting from potential TEAEs, drug dispensation, or other urgent study-related procedures

a The last day of dosing will be at Week 36 visit; subject should consume their last dose of study drug on site, after pre-dose assessments have been completed. The Week 36 visit will also be the ET visit. During the study visit, assessments should be collected from any subject who discontinues study drug or study prematurely.

Early termination visits will have the same procedures as the Week 36 visit, except that study drug will not be administered and trough PK will not be collected.

b The first day study drug is taken is considered Baseline (Day 1). Day 1 assessments should be performed prior to study drug administration. If a subject requires a transfusion on this day, the transfusion may occur only after all study assessments are completed.

c Qualified site personnel will contact the subject by telephone at Week 2 to capture potential TEAEs and concomitant medications. Subjects will also be reminded of compliance with drug and the next visit schedule. If any AEs of significant clinical concern are identified during the telephonic visit, the subject will be requested to come into the site to be assessed.

d Pharmacogenomic evaluation is optional and may be performed at screening if subject provides informed consent.

e Disease history should contain a confirmed diagnosis of β-thalassemia or hemoglobin E/β-thalassemia. Concomitant alpha gene deletion, duplication, or

triplication is allowed. f After obtaining signed informed consent, the subject's transfusion history for the 12 weeks prior to Baseline (Day 1) visit date should be recorded. In order to be eligible for the

study, the dates of transfusion events and the number of pRBC units per event within the 12 weeks prior to the Baseline (Day 1) visit must be available. If available, the following data should also be collected for each transfusion event: volume and hematocrit of each pRBC unit, pre-transfusion Hb, and pre-transfusion weight.

g Vital signs include heart rate, respiratory rate, blood pressure, and body temperature. At Day 1 and Week 3, vital signs will be taken pre-dose and 2 hours (\pm 20 minutes)

post-dose, during the PK assessments. At all other timepoints, vital signs can be taken irrespective of taking study drug. Vital signs should be consistently measured in either the sitting or semi-supine position.

h Transfusion burden will be assessed using the following variables: dates of transfusion events, number of pRBC units per event, volume and hematocrit of each pRBC unit, pre-transfusion Hb, and pre-transfusion weight.

i Complete PEs will be performed at Screening, Week 24, and Week 36 and will include a general examination of the body including the abdomen, heart, lungs, lymph nodes, back/neck, neurological system, skin, extremities, head, eyes, nose, and throat. At all other visits, symptom-directed PEs will be obtained after identification of AEs deemed by the investigator to be of significant clinical concern.

j All ECGs to be performed in triplicate. At Baseline and Week 3, ECGs will be obtained at pre-dose and 2 hours (\pm 30 minutes) post-dose. At all other timepoints, ECGs will be taken pre-dose.

k Females of childbearing potential only. A serum pregnancy test will be performed at screening via a central laboratory; all subsequent tests will be urine performed locally (with test kits provided by the central laboratory).

l Includes HbF and percent F cells. Blood samples should be obtained prior to administration of study drug.

m Includes serum ferritin, soluble transferrin receptor, hepcidin-25, haptoglobin, E-selectin, P-selectin, ICAM-1, VCAM-1, hsCRP, serum NT-proBNP, serum iron and TIBC for calculated transferrin saturation, and erythropoietin. Blood samples should be obtained prior to administration of study drug. PD markers will need to be collected prior to RBC transfusion (if applicable).

n At Baseline and Week 3, serial blood samples for IMR-687 and concentrations of metabolite(s) will be drawn pre-dose (within 30 minutes) and at 15 minutes (\pm 5 minutes), 30 minutes (\pm 5 minutes), and 3 hours (\pm 20 minutes) after administration of study drug. A trough blood sample will be drawn pre-dose at Week 1, Week 24, and Week 36. The date/time of the previous dose will be recorded. If a subject requires a transfusion on the day of a PK draw, the transfusion can only be performed after the final PK sampling. For ET visits, a trough blood sample will not be collected. Patients dosed prior to protocol version 5.0 (15 Mar 2021) used

the following PK sampling schedule: At Baseline and Week 3, serial blood samples for IMR-687 and concentrations of metabolite(s) were drawn pre-dose (within 30 minutes) and at 30 minutes (\pm 5 minutes), 1.5 hours (\pm 15 minutes), 4 hours (\pm 15 minutes), 6 hours (\pm 1 hour) and 24 hours (\pm 2 hours) after administration of study drug. On these full profile PK days, food details were also recorded at the clinical sites. A trough blood sample was drawn pre-dose at Week 1, Week 24, and Week 36. Transfusion should not have coincided with Baseline (Day 1) or the Week 3 visit, due to the PK assessment that day. For ET visits, a trough blood sample was not collected.

- o Quality of life assessments will be assessed by the TranQOL and SF-36 QoL tools. The QoL assessments will be administered at Baseline and at Weeks 12, 24, and 36. Baseline QoL assessments should be completed before administration of study drug.
- p On days when study drug is taken in the clinic, food details will also be recorded.
- q Adverse events and concomitant medications, including iron chelation therapy and hydroxyurea use, will be recorded at each visit throughout the study from Screening (after signing the ICF) through the end of study visit (Week 40).

